11.1.3.2 Exploratory analysis of Adverse Events and Infection Intensity: Logistic regression

A further exploratory analysis will model the log odds of any adverse event using infection intensity (epg) on a continuous scale, treatment, and age group as

predictors. Exposure variables will be modelled as fixed effects with an interaction term between infection intensity and age group.

Logistic regressions for both baseline and 24 month time points will be performed.

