8.3 Covariates and Subgroups

(ICH E3; 9.7.1, 11.4.2.1. ICH E9; 5.7)

School site was used to stratify randomisation and will be adjusted for as a fixed coefficient in the primary analysis.

Baseline Fibrosis score and egg count will be fixed effects in the model.

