9.3 Protocol Deviations

All school-based trial activities were paused on 19th March 2020 in accordance with the Ugandan government announcement concerning COVID-19. Therefore, baseline data for the trial had been collected at different time-points.

Baseline data collected from Buhirigi was collected 17 months after MDA, in March 2020, Baseline data for Kaiso was collected 9 months after MDA, in March 2021.

In order to ensure data integrity a 10% resample of the Buhirigi baseline data was performed in March 2021 for the primary and secondary endpoints.

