10.2.2 Analysis of secondary endpoint – Infection intensity (mean epg)
Analysis of the secondary endpoint will test if there is a difference in the mean infection intensity between the control and each intervention arm as well as between each of the two intervention arms.

A multiple linear regression model will estimate the infection intensity at 24 months for each treatment group adjusted for baseline infection intensity (EPG), and school. A z-test will compare each of the three pairwise comparisons separately and provide a p-value for the probability that a difference in the means produced by the model would be observed purely due to chance.

Note that an additional analysis was added post hoc which modelled the mean infection intensity by treatment group which adjusted for baseline infection intensity and school with an interaction term between treatment group and school.

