16.1.5 Post Hoc analysis added

- a. Multiple linear regression of infection intensity at 24 months on treatment group: This analysis was repeated with an interaction term between school and treatment group.
- b. Logistic regression of the prevalence of infection at 24 months on treatment group. This analysis was repeated to include baseline egg count as a covariate.

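### The exploratory adverse event logistic models omit school, so the egg-count odds ratio can mix the within-school association with a difference between the two sites

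*SAP*

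**What the plan says.** Section 11.1.3.2 describes a further exploratory analysis that "will model the log odds of any adverse event using infection intensity (epg) on a continuous scale, treatment, and age group as" predictors. The only other term is an interaction: "Exposure variables will be modelled as fixed effects with an interaction term between infection intensity and age group". The model is fitted twice: "Logistic regressions for both baseline and 24 month time points will be performed". School does not appear.

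Elsewhere school has a stated role. Section 8.3: "School site was used to stratify randomisation and will be adjusted for as a fixed coefficient in the primary analysis". The 24-month models for mean infection intensity (10.2.2), heavy infection (10.2.3) and prevalence (10.2.5) also adjust for it. For mean intensity, a post hoc model was added, "adjusted for baseline infection intensity and school with an interaction term between treatment group and school"; section 16.1.5 records the same addition.

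On timing, section 9.3 states: "Baseline data collected from Buhirigi was collected 17 months after MDA, in March 2020, Baseline data for Kaiso was collected 9 months after MDA", the latter in March 2021.

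**The concern.** In the efficacy models the contrast of interest is the randomised arm. Randomisation was stratified by school, so leaving school out would not confound that contrast. In 11.1.3.2 the coefficient of interest belongs to egg count, which randomisation does not protect. A factor related to both egg count and the chance of an adverse event will bias it, and school is an obvious candidate.

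Two conditions must hold together: egg counts differ by school, and adverse event rates differ by school for reasons other than egg count. For the first, the baseline timing in section 9.3 makes a difference plausible, since a longer gap since mass treatment leaves more time for reinfection. At 24 months that argument no longer applies. There the only pointers are that the SAP adjusts its own egg-count model for school and later let the arm effect vary by school. For the second condition the SAP gives no information.

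If both hold, the reported odds ratio may show an association that is absent within each school, or hide or reverse one that is present.

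**Working it through.** The SAP gives no figure on this point, so there is none to reproduce. The size has to be shown over assumed inputs.

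**Assumptions (none from the SAP).** Two schools of equal size; log egg count normal within school with SD 1; gap between schools *d* = 0.5 or 1 SD; adverse event rates p₀ and p₁ of 20% vs 30% or 20% vs 40%; no association within school (true odds ratio 1.00); two age groups; three arms.

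**Check by hand.** Ignoring age and arm, which are balanced across schools here, the pooled log odds ratio per SD is approximately

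β ≈ d(q₁ − q₀) / v

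- q₁ = p₁/(p₀ + p₁): the share of children with an event who attend the second school.
- q₀ = (1 − p₁)/(2 − p₀ − p₁): the same share among children without an event.
- v = 1 + d²[w q₁(1 − q₁) + (1 − w) q₀(1 − q₀)], with w = (p₀ + p₁)/2.

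For d = 1 and 20% vs 40%: q₁ = 0.4/0.6 = 0.667; q₀ = 0.6/1.4 = 0.429; v = 1 + 0.3 × 0.222 + 0.7 × 0.245 = 1.238. So β ≈ 0.238/1.238 = 0.192 and the odds ratio is exp(0.192) = 1.21. With the event gap reversed it is exp(−0.192) = 0.83.

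The other settings by the same formula:
- d = 1, 20/30: 0.1333/1.2467 = 0.107, odds ratio 1.11.
- d = 0.5, 20/40: 0.1190/1.0595 = 0.112, odds ratio 1.12.
- d = 0.5, 20/30: 0.0667/1.0617 = 0.063, odds ratio 1.06.

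**Simulation of the SAP's model** (egg count, age group, their interaction, arm; with and without school; 2,000 runs per setting; N = 600; log egg count). The SAP names no test, so the odds ratio is the main result. The rejection rate is for a nominal 5% Wald test of the egg-count term without school, with age coded ±0.5 (centred) or 0/1.

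| Gap in log epg | AE rates | OR per SD, no school | Rejects, centred age | Rejects, 0/1 age |
|---|---|---|---|---|
| 0.5 SD | 20/30% | about 1.06 | 10% | 7% |
| 0.5 SD | 20/40% | about 1.12 | 26% | 15% |
| 1 SD | 20/30% | about 1.12 | 24% | 14% |
| 1 SD | 20/40% | about 1.21 | 65% | 37% |
| 1 SD | 40/20% | 0.82 | 66% | 40% |

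With a school term the odds ratio is 0.99 to 1.01 and rejection is at or below about 6% throughout. The joint 2-df test of egg count and its interaction, which does not depend on age coding, rejects without school in about 8%, 20%, 18% and 54% for the first four rows.

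**Only one gap present.** A 1 SD gap with equal event rates (20/20) rejects in 5.3%; no egg-count gap with 20/40 rejects in 5.2%. Neither shows an excess.

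**Fewer children, or raw counts.** At N = 300 the largest setting rejects in 40% (centred) or 21% (0/1), the smallest in 7% or 6%. If egg count enters untransformed and skewed (lognormal, log SD 1 to 2, N = 600), the largest setting rejects in 14% to 37% (centred) or 6% to 20% (0/1), and the smallest in 3% to 7%, which is no real excess.

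**Hiding or reversing.** With d = 1 and event rates of 40% vs 20% (fewer events in the school with higher counts), a true within-school odds ratio of 1.22 appears as about 0.96, and one of 1.10 as 0.88 to 0.89. The model with school recovers the true values.

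**Other scaling.** A large-sample simulation with SD 2 in ln(epg + 1), school shifts of 0.5 to 1.5 log units and school odds ratios for events of 1.5 to 3 turned a true odds ratio of 1.00 per log unit into 1.01 to 1.09. A school term brought it back to about 1.00.

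**The case against.** The strongest reply is that nothing here contradicts the SAP. Section 8.3 commits to school adjustment for the primary analysis only, and the egg reduction rate model in 10.2.4 has no school term either. The stated objective (5.1.3) is how well infection intensity predicts adverse events, and for prediction, variation between schools is usable information. Both school differences are assumed. The post hoc interaction asks whether the arm effect varies by school, which is different from asking whether egg counts do. The largest effects need several favourable assumptions at once, and the power re-estimate plans for 100 per arm, so N = 300 may be nearer the 24-month reality.

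Much of this stands. The omission is a weak modelling choice and breaks no rule in the SAP; the evidence for 24 months is thin; the size is uncertain. Two parts do not carry. The prediction objective is served by the pooled ROC curves in 11.1.3.1, which this point leaves alone. The logistic model adjusts for arm and age and calls its terms exposures, so its odds ratio will be read as an adjusted association, and with two schools a site component would not transfer elsewhere. The contrasts in 10.2.4 are between randomised arms or within participants, so that model is no precedent.

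A further fair point: section 15.1.1 records a COVID-19 delay between Buhirigi's first baseline collections and dosing. That could change the egg-count slope in that school, which a school main effect would not correct.

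**Conclusion.** The point holds, as something to consider. The model in 11.1.3.2 is fully listed, omits the stratification factor, and estimates the effect of a non-randomised exposure. Distortion requires both egg counts and adverse event rates to differ by school. The SAP makes the first plausible at baseline and is silent on the second. Under the assumed gaps, an absent association would be reported as an odds ratio per SD of about 1.06 to 1.21, or down to 0.82 if the event gap runs the other way. With small gaps, or on raw skewed counts, the effect can be negligible. The primary and secondary endpoints and the adverse event comparisons between randomised arms are unaffected.

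**What to change.** Add school (Buhirigi / Kaiso) as a fixed effect to both logistic models in 11.1.3.2, at baseline and at 24 months. Keep the pooled ROC curves and areas in 11.1.3.1 as planned; school-specific areas are an optional supplement. The cost is one sentence in the SAP and one degree of freedom per model. School is already collected and used in other models, so no new data are needed.

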- A log capturing the version of the software and any external add-on code: used.

15 Summary of Changes to the Protocol

15.1.1 Protocol v 2.0

- Updated CI Maternity Cover (Front page, Section 2 Trial Management Committees and Section 26.3 Safety Reporting Flow Chart)
- Addition of 'school-community based' to aim (Section 7) to enable trial activities to be carried out whilst schools are closed due to COVID-19 National Guidelines
- Addition Section 9 Community School and Trial Team COVID-19 precautions.
- Section 11.1.1.2 removal of IMP expiry date of 31/01/2022, as trial will run beyond this date due to COVID-19 pause of trial activities.
- Addition of 'local community trial site location' and 'house-hold to house-hold' throughout the protocol to enable trial activities to be carried out in the appropriate locations whilst the schools are not permitted to be used for trial activities due to COVID-19 restrictions. (Section 12)
- Explicit statement that trial activities to return to the participating school location when allowed. (Section 12)
- Clarification of exploratory outcome sample collection (Section 12.3.3).
- Addition of participant photograph to enhance participant identification for community based trial activities (Section 12.3.3.1)
- Widening of window between baseline assessments and IMP administration so that baseline data may be used. Delay between activities caused by COVID-19 pause to trial activities. (Section 12.4)
- Addition Section 12.4.1 Baseline Assessment Assurance following COVID-19 Pause. Text added to allow repeat collection of primary and secondary endpoint data from Buhirigi School participants to verify data integrity despite time delay between first collections and IMP administration caused by COVID-19 pause.
- Section 12.5.3 Addition of footnotes to the Schedule of assessments to allow for wider window between ultrasound examination and first IMP administration at baseline visit, due to COVID-19 pause.
- Widening of temperature storage range for collected samples (Section 16)

15.1.2 Protocol v 3.0

Schedule of assessments and Trial assessments following the 1st treatment dose

- Update of 1-year procedures in trial synopsis (section 4) to reflect removal of ultrasound examination and reduction in sampling for egg counts.
- Update of trial flow chart (section 5) to reflect removal of 1-year+4-week egg count for exploratory outcome of egg reduction rate

- Update of section 8.6. Trial outcome measures to reflect altered examinations/sampling schedule detailed above for changes to sections 4 and 5, plus removal of blood sampling at 1-year.
- Update of Schedule of assessment (Section 12.6) to reflect altered examination/sampling schedule detailed above for changes to sections 4 and
- Update of Response Criteria (Section 15.1) to reflect removal of ultrasound examinations at 1-year.

Update of appendix 1 to reflect changes in Data Management responsibilities

15.1.3 Protocol v4.0

Sumbitted to VCD REC prior to NDA approval

- Update of Trial Management Committee (section 2) to reflect change in Trial Management Group
- Update of Trial Synopsis (section 4) with clarification of AE monitoring procedure
- Update of Reporting Serious Advers events (section 13.5) to reflect new SAE reporting structure
- Update of Toxicity (section 14) to reflect change in qualification required for the Trial Site Manager
- Update of Participant registration/ Randomisation procedure (section 26.1.1) to correctly reflect procedure that took place

Update of Safety Reporting Flow Chart (Section 26.4) to reflect changed qualification requirement of Trial Site Manager and where the medical oversight is provided. Sumbitted to VCD REC prior to NDA approval

15.1.4 Protocol v4.1

Administrative change, submitted to VCD REC prior to NDA approval (note – submitted prior to review of version 4)

Update of Trial management committee (section 4) to include name of Trial
 Site manager

Update of Safety Reporting Flow Chart (Section 26.4) to include name of Trial Site manager.

16 Summary of Changes to the SAP

16.1.1 Re-estimation of the power of the study based on a revised prediction of the number of participants remaining in the trail by 2 years

It was felt that the COVID-19 pandemic and missing consent documentation leading to the necessity of re-consenting around 25% of individuals would lead to a much reduced sample size. Therefor a different approach to multiple testing of the primary analysis hypotheses was taken which allowed a 5% alpha to be used.

A revised 100 participants per treatment group was used to estimate the power when the treatment effect was a 20%, 25% and 30% reduction in the primary outcome.

16.1.2 Change to definition of Full Analysis population

Removal of the condition to only include participants 'treated at baseline' in the population. Due to the COVID 19 pandemic many participants were not treated at baseline but were treated at other time points in the trial. Including only participants treated at baseline would significantly reduce the sample size and reduce the power. Also information would be lost for those participants not treated at baseline but treated at other time points

16.1.3 Creation of category A/B for WHO Ultrasonography score

For participants who had real and recorded periportal fibrosis scores recorded as A and B or B and A these participants will be categorised as having a score of A/B in any table reporting on the summary statistics for the WHO Ultrasonography score.

16.1.4 Dealing with missing baseline data for WHO Ultrasonography score and egg

There is a proportion of baseline data missing from the ultrasound and egg counts due to the delayed start of the trial due to the COVID-19 pandemic. Removal of these participants from the data set would potentially lead to removal of outcome data from the analysis models and less efficiency overall. We will impute values for these missing values as described in section 8.4

16.1.5 Post Hoc analysis added

- a. Multiple linear regression of infection intensity at 24 months on treatment group: This analysis was repeated with an interaction term between school and treatment group.
- b. Logistic regression of the prevalence of infection at 24 months on treatment group. This analysis was repeated to include baseline egg count as a covariate.

16.1.6 Baseline Resample comparison – Ultrasonography

This analysis was not performed since all resample data was identical.

16.1.7 Sensitivity Analysis

6 participants who required adjudication of their baseline ultrasonography scores did not receive an adjudicated score as the images required to perform this process could not be located. It was therefor decided that a best case/worst case approach to a sensitivity analysis be performed. A total of 6 additional data sets were created where different possible combinations of the missing baseline scores were added. I of the participants only had one image score and this was used as the adjudicated scores in all data sets. 2 participants did not have final ultrasound data at 24 months and thus were not included in any analysis.

17 References

- 1. Cheever AW. A Quantitative Post-Mortem Study of Schistosomiasis Mansoni in Man. Am J Trop Med Hyg. 1968;17(1):38-64.
- 7. Berhe N, Myrvang B, Gundersen SG. Reversibility of Schistosomal Periportal Thickening/Fibrosis after Praziquantel Therapy: A Twenty-Six Month Follow-up Study in Ethiopia. The American Journal of Tropical Medicine and Hygiene Am J Trop Med Hyg. 78(2):228-34.

- Stef van Buuren. Flexible Imputation of Missing Data. Chapman and Hill.
 2018.
